2.0 Study Objectives

2.1 Primary Endpoints:

To determine if Tarceva, given orally on a daily basis along with concurrent whole brain radiation therapy **improves median survival** of patients with brain metastases, compared with historical controls.

[figure not shown]
2.2 Secondary Endpoints:

- 2.2.1 To see if Tarceva along with concurrent WBRT, improves **quality of life** as assessed with the Spitzer Quality of Life Index (Appendix E) and the Folstein Mini-Mental Status Exam (Appendix F). Optional test will include Digit Span, Digit Symbol, Hopkins Verbal Learning Test, Controlled Oral Word Association, Trail Making Test Part A, Trail Making Test Part B, Grooved Pegboard, Barthel [name]. Anderson Symptom Inventory, and Functional Assessment of Cancer Therapy with Brain Module. As of July 18, 2012- Optional tests will no longer be completed.
- 2.2.2 To see if Tarceva along with concurrent WBRT, influences cause of death compared to matched controls, based on key attributes such as stage, age KPS, number of brain metastasis, etc.
- 2.2.3 To see if Tarceva along with concurrent WBRT, increases time to progression of disease.
- 2.2.4 To sequence the EGFR receptor of patients treated with Tarceva, in order to identify specific gene mutations that may correlate with favorable responses to Tarceva.
- 2.2.5 To study downstream proteins involved in the EGFR cascade such as p-EGFR, Raf, PKC, JNK, and p-AKT. This information will be combined with other protein markers such as E cadherin that appear to increase the probability of response, in the hopes of developing a genetic signature of patients most likely to benefit from this regimen.
- 2.2.6 To confirm the safety profile of Tarceva along with concurrent external beam radiation therapy, in the context of treating central nervous system malignancies.
- 2.2.7 To provide evidence to support a much larger multi-institutional study.

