3.0 Study Design

Twenty patients will be collected from this M.D. Anderson based study and the data will be combined with an identical 20 patient study that [name] started while at the Arizona Cancer Center. The Arizona study has enrolled 15 of the planned 20 patients (as of August 2008), and by combining these two studies we will have a total of 40 patients for final analysis.

Study Schema

Patients must have radiographic evidence of brain metastases, proven with CT or MRI so that we can stratify patients by the number of brain metastases. Additionally, they must have no prior history of cranial radiation (other than stereotactic radiosurgery). Once enrolled, patients will receive Tarceva (150mg PO QD) for at least 6 days prior to starting and during whole brain radiotherapy (WBRT). External beam radiation will consist of opposed laterals to a total dose of 3500cGy in 14 daily fractions.

Upon completion of external whole brain radiation, patients will continue taking Tarceva (150mg PO QD) until documentation of disease progression (unless treating physician feels that stopping Tarceva would adversely affect the patient) or if patients are unable to tolerate study drug due to toxicities. Patients will be allowed to stop taking Tarceva at any time during this trial. Following completion of WBRT patients will have a repeat MRI or CT at 1 month after completion of WBRT, and then at 3 month intervals, or sooner if indicated by symptom progression. Additionally, during active treatment period of this trial, patients will not be allowed to have surgical debulking of CNS tumors, or stereotactic radiosurgery of CNS lesions, as this need would correlate with progression of disease. Patients will be allowed to receive palliative radiation if needed to address symptoms. Patients will be allowed to dose reduce down to 50mg per day, and may also take a treatment break of up to seven days.

Survival will be compared to a database of patients with similar histologies and stratified according to their Recursive Partitioning Analysis (RPA) class and the number of brain metastases, at time of diagnosis (16). The RPA is a predictive tool used to estimate survival based on age, performance status, and presence of extracranial metastasis.

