6.0 Study Methods

Study Calendar

Assessment	Screening	Baseline (1-3 days prior to day 1 of Tarceva)	Weekly During treatment	One Month Post RT (+/- 7 days)	Follow-up for patients on Tarceva (+/- 7 days)	Follow-up for patients off Tarceva (+/- 14 days)^{m,n,o}
-------------------	------------------	--	--	---	---	---

Histological confirmation of NSCLC	X					
CT/MRI of brain and report	X^b			X	X^m	X
CBC/Differential	X^b					
Platelet	X^b					
Complete Metabolic panel)	X^b					
Repeat sodium level			X^e			
CT or PET of Liver	X^c					
Medical History	X	X^d			X^{d,f}	X^d
Physical Examination	X^b		X	X	X^m	X
Concomitant Medications	X	X	X	X	X^{a,f}	
Serum Pregnancy test, if applicable	Xⁱ					

Assessment	Screening	Baseline (1-3 days prior to day 1 of Tarceva)	Weekly During treatment	One Month Post RT (+/- 7 days)	Follow-up for patients on Tarceva (+/- 7 days)	Follow-up for patients off Tarceva (+/- 14 days)^{m,n,o}
Document steroid dose		X	X	X		
Spitzer Quality of Life Index		X^k	X^l			
Folstein Mini-Mental Status Exam		X^k	X^l			
Optional neurocognitive tests ^p		X^k				
Consent for EGFR expression testing (Optional)	X					
Informed Consent	X					
Vital Signs		X		X	X^m	X
Adverse Event Check ^g			X	X	X^f	X
PT/INR if patient on Coumadin	X		X^{h,j}	X^h	X^h	X

a = until 30 days after last dose of Tarceva

b = within 30 days of starting treatment

c = within 3 months of starting treatment

d = update only

e = Patient will have repeat sodium on RT day 7 and RT day 14 if baseline sodium \leq 135 mg/dl

f= Patients will be seen by the research nurse monthly while on Tarceva (+/- 7 days), and/or one month post last dose of Tarceva (+/- 7 days). Patients on Tarceva, who are unable to return for their follow up visits and 1 month post last dose of Tarceva visit, will be contacted by the research nurse by phone to review/asses the following; Update of medical history, assessment of AE's concurrent medications. They will return their unused Tarceva medication along with their medication diaries to the research nurse via mail.

- g= All adverse events will be collected until 30 days after the last study dose of Tarceva or 30 days post RT visit (whichever is last), then only neurocognitive decline will be captured.
- h = Only if patient has abnormal values during initial screening testing
- i= within 7 days of starting protocol treatment
- j= weekly until stable
- k= Prior to radiation
- l = During last week of radiation therapy (+/- 7 days)

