- m= every 3 months (+/- 14 days) for 2 years then every 6 months after
- n= patients with deteriorating conditions who are unable to return may be followed up by telephone. MRI brain, physical exam, mini-mental exam, QOL Index and neurocognitive testing may be excluded.
- o= for patients with progressive CNS disease we will record survival only.
- p= Optional neurocognitive tests will include Digit Span, Digit Symbol, Hopkins Verbal Learning Test, Controlled Oral Word Association, Trail Making Test Part A, Trail Making Test Part B, Grooved Pegboard, Barthel [name]. Anderson Symptom Inventory, and Functional Assessment of Cancer Therapy with Brain Module. As of July 18, 2012- Optional tests will no longer be completed.

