6.2 Study Discontinuation

Once enrolled in this study, patients will be allowed to discontinue Tarceva at anytime during this study, before, during or after radiation and be considered "off active treatment". If for any reason a patient wishes to discontinue taking Tarceva they will be allowed to do so. Patients will also be allowed to stop radiation at anytime as well; however, doing so will preclude them from continuing to receive Tarceva. Patients will be allowed to have a drug break of up to seven days; however, longer breaks may lead to removal from the study based on the discretion of principal investigator. Additionally the principle investigator may choose to discontinue a patient at any time. All reasons for discontinuation of treatment must be documented. Patients will be considered "on active treatment" while they are taking Tarceva. Once Tarceva is stopped patients will be defined as "off active treatment" and will still undergo routine follow up and screening as per the study calendar (see section 6.0). If after disease progression the patient's treating physician feels it is in the best interest of the patient to continue Tarceva, they may do so and the patient may also receive other therapies while continuing the study drug Tarceva without having the patient terminated from the study. Monitoring and follow up will continue as per the study calendar (see section 6.0).

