8.0 Adverse Events

All adverse events will be graded according to NCI CTC version 3.0

Adverse drug experience means any adverse event associated with the use of a drug in humans, whether or not considered drug related, including the following: an adverse event occurring in the course of the use of a drug product in professional practice; an adverse event occurring from drug overdose, whether accidental or intentional; an adverse event occurring from drug abuse; an adverse event occurring from drug withdrawal; and any failure of expected pharmacological action (21 CFR 314.80).

An adverse event is any adverse change from the subject's baseline condition, including any clinically significant laboratory test value abnormality that occurs during the course of the clinical study after the informed consent is signed, whether the adverse event is considered related to the treatment or not.

All adverse events will be collected until one month post last day of Tarceva or radiation (whichever is last). This may require obtaining clinical blood samples for appropriate laboratory tests until their values return to baseline levels or performing follow-up physical examinations until resolution of identified abnormalities.

The most common adverse reactions in patients receiving single-agent TARCEVA 150 mg were rash and diarrhea. Grade 3/4 rash and diarrhea occurred in 9% and 6%, respectively, in TARCEVA-treated patients. Rash and diarrhea each resulted in study discontinuation in 1% of TARCEVA-treated patients. Six percent and 1% of patients needed dose reduction for rash and diarrhea, respectively. The median time to onset of rash was 8 days, and the median time to onset of diarrhea was 12 days.

	TARCEVA 150 mg N = 485			Placebo N = 242		
NCI CTC Grade	Any Grade	Grade 3	Grade 4	Any Grade	Grade 3	Grade 4
MedDRA Preferred Term	%	%	%	%	%	%
Rash	75	8	<1	17	0	0
Diarrhea	54	6	<1	18	<1	0
Anorexia	52	8	1	38	5	<1
Fatigue	52	14	4	45	16	4
Dyspnea	41	17	11	35	15	11
Cough	33	4	0	29	2	0
Nausea	33	3	0	24	2	0
Infection	24	4	0	15	2	0
Vomiting	23	2	<1	19	2	0
Stomatitis	17	<1	0	3	0	0
Pruritus	13	<1	0	5	0	0
Dry skin	12	0	0	4	0	0
Conjunctivitis	12	<1	0	2	<1	0
Keratoconjunctivitis sicca	12	0	0	3	0	0
Abdominal pain	11	2	<1	7	1	<1

Rare, But Serious

In some patients taking erlotinib and oral blood thinners INR have been reported abnormally elevated. The elevation of INR was associated with bleeding.

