11.5.1 Endpoint Analysis

11.5.1.1 Survival

We will use the product limit estimator of Kaplan and Meier (1958) to estimate the overall survival of all patients using the intent-to-treat principle. We will report the median survival and its associated 95% confidence interval.

We will also estimate overall survival stratified by treating institution and class, as described above in section 11.2.

We will compare the estimates of survival from this study with a recent reported phase III randomized RTOG trial, 0118, which randomized 332 patients to WBRT with or without Thalidomide (19). Our patients will be compared to both the overall survival and CNS progression free survival from this study.

We will tabulate cause of death by treating institution and by class, and we will compare the cause of death for patients in this study with patients from RTOG 01188.

We will analyze progression-free survival (PFS) in the same manner as overall survival.

We will use the methods described in Klein and Moeschberger (1997) to test for differences in survival between the matched pairs. To help us understand how similar/dissimilar patients from MDACC and Arizona are we will summarize the demographic and clinical characteristics of these patients separately. We will also estimate the survival of the 40 patients (20 from MDACC and 20 from AZCC) with the product-limit estimator of Kaplan and Meier (1958) stratified by study center (MDACC, AZCC), and we will use Cox (1972) proportional hazards regression to model survival of these 40 patients as a function of study center and estimate the hazard ratio (MDACC:AZCC) with a 95% confidence interval. For the match control based variables we will use patients from a prior randomized whole brain radiation therapy (WBRT) study performed by the Radiation Therapy Oncology Group (RTOG) study (RTOG 0118). Patients will be matched based on age, KPS, number of brain metastasis and control of systemic disease. If there is more than one match available for a patient we will review all cases.

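### Footnote o records only survival after CNS progression off Tarceva, so cause of death, a secondary endpoint, is not secured in that group

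*Combined protocol and SAP*

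**What the plan says.** The Study Calendar in section 6.0 has separate follow-up columns for patients on and off Tarceva. The off-Tarceva column heading carries footnotes m, n and o; the on-Tarceva heading does not. Footnote o reads "for patients with progressive CNS disease we will record survival only".

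Objective 2.2.2 asks whether the treatment "influences cause of death compared to matched controls". Section 11.5.1.1 turns this into two analyses. The first is a table of causes for each site and each RPA class. The second is the external comparison: "we will compare the cause of death for patients in this study with patients from RTOG 01188" (the trial is given elsewhere in that section as RTOG 0118). Neither analysis is limited to patients without CNS progression.

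A related pair of passages concerns therapy after progression. Section 3.0 says that in the active treatment period "patients will not be allowed to have surgical debulking of CNS tumors, or stereotactic radiosurgery of CNS lesions". Section 6.2 defines a patient taking Tarceva as being on active treatment, yet says that after progression "the patient may also receive other therapies while continuing the study drug Tarceva without having the patient terminated from the study".

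**The concern.** The only explicit recording instruction for patients off drug with CNS progression leaves out an item that a secondary endpoint needs. Patients with progressing brain disease are plausibly the ones more likely to die of it. If their cause of death is dropped and other patients' is kept, the missingness is tied to the outcome itself. The tabulation by institution and class, and the comparison with RTOG 0118, would then rest on a selected set of deaths. With so few deaths in total, even a moderate number of unknown causes would leave the neurological share poorly determined.

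**Working it through.** **Step 1. Which deaths have a route to a recorded cause?**

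- *On Tarceva, including after progression.* Footnote o does not apply, and 6.2 keeps these patients on calendar follow-up.
- *Off Tarceva, up to 30 days after the last dose.* Death is a serious adverse event outcome. Section 8.2 captures serious events to 30 days after the last dose of study treatment and requires a written report of fatal events whatever the attribution. These deaths should be documented.
- *Off Tarceva, later than 30 days, with CNS progression.* Section 8.2 then covers only treatment-related events. Footnote g and section 6.4 reduce adverse-event capture to neurocognitive decline. Footnote o reduces recording to survival. No rule asks for cause.

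The third group may be large, because progression is the default reason to stop Tarceva (3.0, 5.6). CNS progression therefore usually moves a patient into the column that carries footnote o.

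**Step 2. How many deaths are expected?**

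Inputs from 11.3: N = 40, medians 4.2 and 6.0 months, uniform accrual over 24 months, 9 further months of follow-up, exponential survival, one-sided alpha 0.10.

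- Hazard under the target: L = ln 2 / 6.0 = 0.1155 per month.
- P(death) = 1 - [exp(-9L) - exp(-33L)] / (24L) = 1 - (0.3536 - 0.0221) / 2.7726 = 0.880.
- Expected deaths: 40 × 0.880 = 35.2.
- Check against the plan: power = Φ(√35.2 × ln(6.0/4.2) - 1.2816) = Φ(2.117 - 1.282) = 79.8%. This reproduces the stated 80%.

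**Step 3. How many could lack a cause?**

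The documents do not give the share f of deaths in the third group. As an assumption, take f from 20% to 50%:

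- 0.20 × 35 = 7 deaths
- 0.30 × 35 = 10.5, about 11 deaths
- 0.50 × 35 = 17.5, about 18 deaths

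This counts both sites. It assumes that the Arizona study, which 3.0 calls identical, has the same recording rule. If only the 20 MD Anderson patients are affected, expected deaths there are 20 × 0.880 = 17.6, and the range is about 4 to 9.

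**Step 4. What could this do to the neurological share?**

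If the true share is q, and the share among deaths without a recorded cause is u, the share among recorded deaths is (q - f·u) / (1 - f). This is below q whenever u exceeds q. An illustration with q = 40%, all values assumed:

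| f | u = 50% | u = 70% |
|---|---|---|
| 20% | 37.5% | 32.5% |
| 30% | 35.7% | 27.1% |
| 50% | 30.0% | 10.0% |

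The table shows the direction and how sensitive the result is. It does not estimate the bias in this trial.

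**The case against.** The strongest reply is that footnote o belongs to a visit calendar. It sits beside footnote n, which excuses deteriorating patients from assessments, so it may mean only that visits stop and survival follow-up goes on. Cause could still be noted with the date of death. The calendar has no cause-of-death row for any patient, so if 11.5.1.1 is enough to secure the item for other patients, it should be enough here too.

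Part of this stands: the documents do not prove that cause of death will be missing. But 11.5.1.1 states an analysis and gives no rule for collecting the data, whereas footnote o is an explicit recording rule, and it is restrictive. Staff who follow it as written would not record cause in this group, while nothing tells them to leave it out in others.

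A reader might infer three stronger points, which the documents do not support.

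- *That the 30-day adverse-event window is cut short.* The contact one month after the last dose is set by footnote f in the on-Tarceva column, which does not carry footnote o. Footnote g and section 8.0 state the window with no exception for CNS progression.
- *That later therapy is not captured in patients kept on Tarceva.* Footnote o does not reach them. Section 6.1 has prescribed treatments recorded on the case report form and concomitant medications tracked to one month after the last dose.
- *That the comparison is biased in favour of the treatment.* This would need more complete cause-of-death data in the RTOG 0118 patients, and unknown causes silently dropped. The documents state neither.

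On 3.0 and 6.2, one can argue that the first is the general rule and the second an exception after progression. That reading is possible, but both passages depend on the term active treatment and neither refers to the other, so the wording still needs to be reconciled.

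**Conclusion.** The conflict is real and limited. Footnote o is at odds with objective 2.2.2 and section 11.5.1.1. Cause of death is not secured, and on a literal reading is excluded, for deaths after CNS progression that occur off drug and more than 30 days after the last dose, unless treatment-related. The neurological share among recorded deaths could be too low. That direction rests on the plausible but undocumented assumption that neurological death is more frequent in this group. The documents do not allow the size of the error to be estimated. The figure of roughly 7 to 18 deaths without a cause, out of about 35, depends on the assumed 20-50% and on the same rule applying at both sites.

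Only a secondary endpoint is involved. Survival is still recorded in every patient, so the primary endpoint, sample size and power are unaffected. The change should be made because it is cheap and because cause of death is harder to recover later.

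**What to change.** Amend footnote o so that, for patients with progressive CNS disease, both the date and the cause of death are recorded, with follow-up for these items until death. The existing survival contact or a chart review can supply them. If survival was always meant to include cause, one sentence saying so settles the point.

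In 11.5.1.1, state that unknown cause will be its own category in the tabulation and in the RTOG 0118 comparison, so that the extent of missing data is visible.

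Separately, reconcile the wording of 3.0 and 6.2 on therapies after progression in patients still taking Tarceva. Which rule should apply is for the investigators to decide.

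The cost is a short amendment and one extra field per death. No extra visits or patients are needed.

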6.1 Concomitant Medications

The Investigator will be permitted to prescribe treatment(s) at his or her discretion, which must be recorded on the Case Report Form (CRF). All concomitant meds will be tracked until 1 month post last dose of Tarceva.

6.2 Study Discontinuation

Once enrolled in this study, patients will be allowed to discontinue Tarceva at anytime during this study, before, during or after radiation and be considered "off active treatment". If for any reason a patient wishes to discontinue taking Tarceva they will be allowed to do so. Patients will also be allowed to stop radiation at anytime as well; however, doing so will preclude them from continuing to receive Tarceva. Patients will be allowed to have a drug break of up to seven days; however, longer breaks may lead to removal from the study based on the discretion of principal investigator. Additionally the principle investigator may choose to discontinue a patient at any time. All reasons for discontinuation of treatment must be documented. Patients will be considered "on active treatment" while they are taking Tarceva. Once Tarceva is stopped patients will be defined as "off active treatment" and will still undergo routine follow up and screening as per the study calendar (see section 6.0). If after disease progression the patient's treating physician feels it is in the best interest of the patient to continue Tarceva, they may do so and the patient may also receive other therapies while continuing the study drug Tarceva without having the patient terminated from the study. Monitoring and follow up will continue as per the study calendar (see section 6.0).

6.3 Efficacy Evaluations

MRI, or CT, Spitzer Quality of Life Index (Appendix E), Folstein Mini-Mental Status Exam (Appendix F) will be done every three months. As of 2-14-13, MMSE and Spitzer QOL evaluations will no longer be completed.

6.3.1 Optional Neurocognitive tests: As of July 18, 2012, we will no longer be completing optional neurocognitive testing.

The characteristics of a clinical trial battery to assess cognitive function, symptoms, and QOL must include the following: (20) brief ,i.e., able to be completed within 45 minutes by most patients, including those feeling ill, (21) sensitive to changes in patient function with results uninfluenced by prior exposure to the tests ,and (22) inexpensive. We have developed such a battery; the time to complete the cognitive assessment is on average 23 minutes and we have demonstrated that the assessment is practical in terms of cost and burden to patient, and is insensitive to repeated administration (20).

Neuropsychological assessments will be conducted prior to treatment and at designated intervals. Based on similar studies, we anticipate that more than 90% of patients will be willing to participate. Patients who have progressive disease will be followed as long as they are receiving treatment for their disease. At each time point, the test battery described below will be repeated and correlative studies will be obtained.

The following tests were selected because they are widely-used standardized psychometric instruments that have been shown to be sensitive to the neurotoxic effects of cancer treatment in other clinical trials. The tests have published normative data that takes into account age, and where appropriate, education and gender. The tests were also selected to minimize the effects of repeated administration. Data obtained on other studies reveals that patients tend to perform normally on tests of attention span, reflecting adequate effort is being put forth, and that mood disturbance does not correlate with the results of the cognitive portion of the battery. The memory test has six alternate forms. The other tests measure motor and information processing speed and are relatively resistant to the effects of practice. The total time for test administration, including the QOL and symptom measures, is less than 40 minutes.

Cognitive Function
Attention span

Test
Digit Span (21)

Graphomotor speed	Digit Symbol (21)
Memory	Hopkins Verbal Learning Test (22)
Verbal fluency	Controlled Oral Word Association (23)
Visual-motor speed	Trail Making Test Part A (24)
Executive Function	Trail Making Test Part B (24)
Motor dexterity	Grooved Pegboard (24)

Symptoms

Activities of daily living	Barthel ADL Index (25)
Symptoms	M.D. Anderson Symptom Inventory (26)

QOL

Quality of life	Functional Assessment of Cancer Therapy with Brain Module (27)
-----------------	--

Statistical Considerations

We will determine the difference between the pre-treatment baseline and follow-up assessment scores by the reliable change (RC) index (28). This index is derived from the standard error of measurement (SEM) for each test in the battery. One advantage of this statistic is that the baseline level of performance of a given individual is accounted for, since these values may vary from patient to patient.

The SEM is calculated from the test-retest reliability (r) and the standard deviation of test scores (SD): $SEM = SD(1-r)^{1/2}$. The standard error of difference is then calculated: $SE_{diff} = [2(SEM^2)]^{1/2}$. A reliable change (RC) in test scores from baseline to follow-up is considered significant if it falls within a 90% confidence interval that does include zero. For each subject the difference between the pre-treatment baseline and each follow-up assessment will be coded (according to the RC index) as 1 (deterioration), 2 (no change), and 3 (improved). Cross tabulations between this variable, time, and possibly treatment group (to account for multi-arm studies) will be used to examine the percentages of patients in each treatment group that show meaningful losses or gains in the various test domains over the course of the study.

One disadvantage of using the RC approach, however, is that the magnitude of change is not captured. Therefore, we plan to supplement our repeated measures analysis using raw scores.

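### The reliable-change rule for the optional neurocognitive battery is stated backwards, so small changes count as significant and large ones do not (low materiality)

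*Combined protocol and SAP*

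**What the plan says.** The statistical paragraph of section 6.3.1 builds a reliable change (RC) index for the optional battery. It computes a standard error of measurement from each test's SD and test-retest reliability r, and from that a standard error of the difference, SE_diff. It then says a change is "considered significant if it falls within a 90% confidence interval that does include zero". Each follow-up score is coded against baseline as 1 for deterioration, 2 for no change or 3 for improvement. The codes are cross-tabulated to "examine the percentages of patients in each treatment group that show meaningful losses or gains in the various test domains". The section adds that the RC approach loses the size of the change, so raw scores will also be analysed.

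On whether the battery is still in use, the same section says: "As of July 18, 2012, we will no longer be completing optional neurocognitive testing". Section 2.2.1 and the study calendar footnotes repeat this. None of them withdraws the RC analysis of data already collected.

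**The concern.** An interval for a change that includes zero means the change cannot be told apart from measurement error. The rule therefore names the unreliable changes as the significant ones. It also contradicts the paragraph around it, which wants code 2 to mean no change and codes 1 and 3 to mean meaningful loss or gain.

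If the sentence were programmed as it stands, the tables would show most stable patients as changed and most patients with a large decline as unchanged. These tests are listed under the quality-of-life secondary endpoint (section 2.2.1), so the tables could reach a report.

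**Working it through.** **Does the reading of the interval matter?** Take c = 1.645 for a two-sided 90% interval. Two-sided is an assumption, supported by the coding of both directions.

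- Interval centred on the observed change: change ± c × SE_diff includes zero when |change| ≤ c × SE_diff.
- Interval centred on zero: the change falls within ± c × SE_diff when |change| ≤ c × SE_diff.

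Both readings give the same condition, which is that of no reliable change.

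**Inputs.** The 90% level and SE_diff = √(2 × SEM²), with SEM = SD × √(1 − r), come from section 6.3.1. No SD or r is given for any test. For assumed r of 0.6, 0.7, 0.8 and 0.9, the cut-off c × √(2(1 − r)) is 1.47, 1.27, 1.04 and 0.74 SD. The reversal does not depend on r, so the rest is in SE_diff units.

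**Model.** Observed change divided by SE_diff, signed so that negative is worse, is normal with mean −d and variance 1, where d is the true decline. Direction is read from the sign. Changes that do not meet the rule are coded 2.

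- Literal rule: deteriorated = Φ(d) − Φ(d − c); improved = Φ(d + c) − Φ(d); no change = the rest.
- Usual rule: deteriorated = Φ(d − c); improved = Φ(−d − c); no change = the rest.

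For example, at d = 2 the literal rule gives Φ(2) − Φ(0.355) = 0.977 − 0.639 = 0.338 deteriorated. The usual rule gives Φ(0.355) = 0.639.

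| True decline d (SE_diff) | Literal: worse / no change / better | Usual: worse / no change / better |
|---|---|---|
| 0 | 0.450 / 0.100 / 0.450 | 0.050 / 0.900 / 0.050 |
| 1 | 0.582 / 0.264 / 0.155 | 0.260 / 0.736 / 0.004 |
| 2 | 0.338 / 0.639 / 0.023 | 0.639 / 0.361 / 0.000 |
| 3 | 0.086 / 0.912 / 0.001 | 0.912 / 0.088 / 0.000 |

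The total flagged under one rule is the complement of the total under the other: 0.900 v 0.100 at d = 0, and 0.088 v 0.912 at d = 3. The proportion coded as deteriorated is equal where Φ(d) = 2Φ(d − c), at d of about 1.57 (0.47 each). Below that the literal rule over-codes deterioration; above it, it under-codes it. In each row with true decline, coded losses still exceed coded gains.

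**As counts, with no true change.** Section 3.0 sets 20 patients for the MD Anderson study. Per test and time point, the expected number flagged is 20 × 0.9 = 18 v 20 × 0.1 = 2. Twenty is an upper bound for this site. For one stable patient across the 10 listed instruments, taking one score each, it is 10 × 0.9 = 9 v 10 × 0.1 = 1. These are expectations, so independence between tests is not needed.

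**How much data is affected?** This is unknown. The calendar marks the battery only in the baseline column, with the footnote "k= Prior to radiation". Section 6.3.1 says "Neuropsychological assessments will be conducted prior to treatment and at designated intervals" but does not list the intervals. Calendar footnote n lets neurocognitive testing be omitted for deteriorating patients followed by telephone, which suggests follow-up testing was otherwise expected.

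**The case against.** The strongest reply is that this is a slip of one word. The named index, the SE_diff formula, the three codes and the stated aim all point to the usual rule, so a competent analyst would apply that. The figures above arise only if someone programs the sentence literally. The reach is also small: the output is descriptive, with no test or decision attached; section 11 never uses the RC codes; and the raw-score analysis would show real change even if the coding were wrong. The reference to multi-arm studies in a single-arm trial suggests generic text. An optional battery that ended in July 2012, in patients for whom section 11.3 assumes a median survival of 4.2 to 6.0 months, may have few follow-up pairs.

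Most of this stands, and it is why the point ranks low. It does not remove the error. The sentence is the only operative rule behind the codes, and the raw-score analysis does not repair the percentages in the cross-tabulations. Inserting a 'not' would still leave the unclear 'falls within', so the rule is better stated outright. It is fair to say that the scoring-direction line and the count of pairs suggested below go beyond correcting the error; they are useful but secondary.

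**Conclusion.** The rule is wrong as written, and no other section corrects it. The direction of the error follows from the sentence alone. Its size, 90% v 10% flagged when nothing has changed and 34% v 64% coded as deteriorated at a true decline of 2 SE_diff, assumes a two-sided interval, normal measurement error and literal application. Only optional-battery data collected before July 18, 2012 are exposed. Survival and the Mini-Mental and Spitzer analyses are untouched. This is worth correcting, but it threatens no main conclusion of the trial.

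**What to change.** Replace the decision sentence in section 6.3.1 with wording such as:

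> A change is significant if the 90% interval around it (change ± 1.645 × SE_diff) excludes zero, that is, if |change| > 1.645 × SE_diff; otherwise it is coded 2 (no change). Deterioration and improvement follow each test's own published scoring direction.

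Beside the tables, state how many baseline/follow-up pairs they rest on. The cost is one sentence in the plan and one count in the report. No new data are needed and no other analysis changes. If tables have already been produced, confirm which rule was programmed.
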